6.1.4 Treatment arms/group

This is a single-arm study. However, the PET/CT scan sequences for each participant will be assigned at random in a 1:1 ratio after enrolment:

- Sequence 1: [18F]CTT1057 (investigational imaging agent of interest) followed by [68Ga]Ga-PSMA-11 (as part of CTS [if required] and for secondary endpoint).
- Sequence 2: [68Ga]Ga-PSMA-11 (as part of CTS [if required] and for secondary endpoint) followed by [18F]CTT1057 (investigational imaging agent of interest).

Please refer to Section 6.3.2 for assignment details.

6.1.5 **Treatment duration**

The planned duration of treatment period (i.e. single-dose administration of the 2 PET imaging agents) is at least 2 weeks, with single i.v. injection performed at Day 1 and approximately at Day 15. Participants may be discontinued from treatment due to unacceptable toxicity following the first administered imaging agent or at the discretion of the investigator or the participant. Upon end of treatment and the study, participants may be treated with any other medications per discretion of the treating physician.

6.2 Other treatment(s)

6.2.1 **Concomitant therapy**

All medications, procedures, and significant non-drug therapies (including physical therapy and blood transfusions) administered after the participant was enrolled into the study must be recorded on the appropriate Case Report Forms.

Each concomitant drug must be individually assessed against all exclusion criteria/prohibited medication. If in doubt, the investigator should contact the Novartis medical monitor before randomizing a participant or allowing a new medication to be started. If the participant is already enrolled, contact Novartis to determine if the participant should continue participation in the study.

Use of diuretics (e.g. furosemide) to help subject to void before PET/CT scan imaging acquisition is allowed in case of need, upon the discretion of the investigator.

6.2.2 Prohibited medication

Any medication, therapy or procedure (other than the study treatment) that may interfere with PSMA PET imaging is not allowed. Prior to completing both PET imaging scans and CTS procedures, any ADT including LHRH analogues (agonists or antagonists) as well as antiandrogens (both first and second generation compounds) and 5-alpha reductase inhibitors are prohibited. Any therapy/procedure that could interfere with PET PSMA imaging is not allowed.

6.3 Participant numbering, treatment assignment, randomization

6.3.1 Participant numbering

Each participant is identified in the study by a Participant Number (Participant No.), that is assigned when the participant is enrolled for screening and is retained for the participant throughout his participation in the trial. A new Participant No. will be assigned at every subsequent enrollment if the participant is re-screened. The Participant No. consists of the Center Number (Center No.) (as assigned by Novartis to the investigative site) with a sequential participant number suffixed to it, so that each participant's participation is numbered uniquely across the entire database. Upon signing the informed consent form, the participant is assigned to the next sequential Participant No. available.

A new ICF will need to be signed if the investigator chooses to re-screen the participant after a participant has screen failed, and the participant will be assigned a new Participant No.

6.3.2 Treatment assignment, randomization

The IRT will be used to assign the PET/CT scan sequence to each eligible participants at random (1:1 ratio), and the randomization numbers will be stored in IRT. The investigator or his/her delegate will contact the IRT after confirming that the participant fulfills all the inclusion/exclusion criteria.

The investigator or his/her delegate will order [18F]CTT1057 or [68Ga]Ga-PSMA-11 dose prior to the scheduled dosing date (refer to Pharmacy Manual). Each administration will be tracked by the investigator or his/her delegate via IRT. Detailed instructions of Investigational Medicinal Product (IMP) ordering and IRT use will be provided in the Pharmacy Manual.

6.4 Treatment blinding

Novartis

Treatment and PET/CT scan sequence assignment will be open to participants, investigator staff, persons performing the assessments, and the study team. The following blinding is applicable in this study:

- [18F]CTT1057 PET/CT images will be submitted to a CRO for independent centralized read by 3 independent readers blinded to patient data collected in clinical database (such as medical history details or diagnostic test results).
- In addition, [18F]CTT1057 PET/CT images will be read by local nuclear medicine physician or radiologist with expertise in reading oncology PET/CT scans at each site, who will be blinded to [68Ga]Ga-PSMA-11 PET/CT imaging results, but not to other patient data. The results will be shared with the treating physician / Clinical Study Investigator to support the completion of the patient management questionnaire 2.
- Images from diagnostic procedures included in the CTS Level 2 will be submitted to a CRO for independent centralized read by independent readers, blinded to [18F]CTT1057 PET/CT images, but not to other patient data collected in clinical database.
- In addition, these CTS images will be read by a local nuclear medicine physician or radiologist with expertise in reading oncology PET/CT scans at each site as per SoC, who will be blinded to [18F]CTT1057 PET/CT imaging results, but not to other patient data.
- In the cases where pathology will be available, assessments by the local pathologists will be performed as per SoC. Pathologists will be blinded to any PSMA-PET data (i.e. both PET/CT scans).

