
Anatomically localized positive lesions in [18F]CTT1057 PET/CT and the applicable SoT from the hierarchical CTS will be considered true positives for the region-level correct localization rate (CLR, i.e. region-level PPV) and patient-level PPV calculations as the co-primary endpoints of the study.

In the cases where pathology will be available, it will be used as SoT (CTS Level 1). Pathology may be available in case of identified lesions that can be either biopsied or suitable for salvage surgery (in case of solitary or few localized lymph nodes). Local pathologists who will be blinded to any PSMA-PET data (i.e. both PET/CT scan results) will assess the tissue specimens as per SoC (see Section 6.4 for blinding details)

If pathology is not available for a lesion, inconclusive or negative (for biopsy only), CTS Level 2 (imaging diagnostic procedures) will be used as SoT. These must include at least a highresolution CT scan with i.v. and oral contrast (or MRI if CT scan with contrast is medically contraindicated) and a [68Ga]Ga-PSMA-11 PET/CT scan, but will include also any other imaging diagnostic procedures clinically indicated for each patient as per SoC. In order to reduce variability of image readings across multiple study sites, a centralized reading of these imaging diagnostic procedures will be performed in a CRO by 3 readers who will be blinded to [18F]CTT1057 PET/CT scan results, but not to other patient data. The majority rule (2/3 readers) will be used as a final outcome of the reads. Further details will be provided in the imaging charter. See also Section 6.4 and Section 8.3 for blinding and reading details.

If neither of the two first CTS components (i.e. pathology or imaging) are feasible, conclusive or deemed appropriate, then CTS Level 3 (50% or greater decline in PSA following radiation therapy (as long as no concomitant androgen deprivation therapy (ADT) is given) as per PCWG3 criteria) will be used as SoT. The lesion on the [18F]CTT1057 PET/CT scan that was irradiated will be classified as a TP in case of ≥50% PSA decrease 3 months after RT, or as FP otherwise.

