8.3.1 Imaging for tumor assessment

The imaging assessment collection plan for this study is presented in Table 8-2.

Protocol No. CAAA405A12301

Table 8-2 Imaging Assessment Collection Plan

Imaging procedures	Mandatory or Optional	Image Acquisition Timing
[¹⁸ F]CTT1057 PET/CT	Mandatory - all participants	Day 1 or Day 15*
[⁶⁸ Ga]Ga-PSMA-11 PET/CT	Mandatory - all participants	Day 1 or Day 15*
High Resolution CT with i.v. and Oral Contrast (or MRI if CT scan with contrast is medically contraindicated) of at least Chest Abdomen and Pelvis (and any additional region as clinically indicated)	Mandatory - all participants	+/- 8 weeks from [18F]CTT1057 PET/CT Acquisition
Other Standard of Care Imaging diagnostic procedures (MRI, Bone Scan, PET with other imaging agents, etc.)	As clinically indicated per SoC	+/- 8 weeks from [18F]CTT1057 PET/CT Acquisition
Follow-up Standard of Care Imaging diagnostic procedures (CT, MRI, Bone Scan, PET with other imaging agents, etc.)	If clinically required per SoC for the diagnosis of particular lesion(s)	3 months after the initial imaging procedure performed

^{*}Day 1 or 15 determined by participant's randomization into sequence 1 or 2.

Imaging diagnostic procedures (CT/MRI, bone scan, or other modalities) should be performed as clinically indicated for each patient per SoC within 8 weeks (either before or after) the [18F]CTT1057 PET/CT scan. Any imaging assessments already completed during the regular work-up of the participant within 8 weeks prior to [18F]CTT1057 PET/CT scan, including before signing the main study ICF, can be considered as part of imaging component of the CTS Level 2.

CTS Level 2 will be used as reference for co-primary endpoints if pathology is not available for a lesion, inconclusive or biopsy is negative.

The CTS level 2 imaging diagnostic procedures must include at least a high-resolution CT scan with i.v. and oral contrast (or MRI if CT scan with contrast is medically contraindicated) and the [68Ga]Ga-PSMA-11 PET/CT scan. It may include also any other imaging diagnostic procedures clinically indicated for each participant as per SoC (including three-month follow-up imaging where it is clinically required for the diagnosis of particular lesion(s)). A centralized reading of these imaging diagnostic procedures will be performed in a CRO by 3 readers who will be blinded to [18F]CTT1057 PET/CT scan results, but not to other patient data collected in

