clinical database. The majority rule (2/3 readers) will be used as a final outcome of the reads. Further details will be provided in the Imaging Charter.

In addition, the imaging diagnostic procedures included in CTS level 2 will be read by local nuclear medicine physicians or radiologists with expertise in reading oncology PET/CT scans as per SoC, who will be blinded to the [18F]CTT1057 PET/CT scan results, but not to other patient data.

The criteria to be

applied for PET positivity are detailed in Section 4.1.

SoC imaging data to be documented in eCRF will include the outcome of assessments, i.e. if negative or positive for PCa tumor or metastases, regions where lesions are identified, number and location of the lesions. For lesions that are visually positive on the [68Ga]Ga-PSMA-11 PET but not considered as PCa, their characteristics will be documented (i.e. non-prostate cancer tumoral or benign, such as inflammatory, degenerative, necrotic, other). For CT/MRI lesion size measurements RECIST 1.1 guidelines will be applicable (Section 16.2).

Post-baseline PET imaging assessments

PET imaging assessments as described in Table 8-1 should be performed at the timepoints, at Day 1 and approximately at Day 15. The following steps will take place on each PET imaging day:

[68Ga]Ga-PSMA-11 PET imaging day (as part of the imaging component of CTS):

- 1. Participant will be asked to drink 1-2 glasses of water before arrival at the clinic
- 2. Participants will be weighed and vital signs (body temperature, blood pressure, heart rate, respiratory rate) will be recorded prior injection.
- 3. Participant will be injected i.v. with a single dose of approximately 150 MBq of [68Ga]Ga-PSMA-11, administered doses must not be lower than 111MBq or higher than 185MBq in any case then flushed by 10 ml of saline. For [18F]CTT1057 administration, please see below
- 4. Vital signs (body temperature, blood pressure, heart rate, respiratory rate) will be recorded after the injection
- 5. Participant will void immediately prior to the scan. If it is not possible for the patient to void, an urethral catheterization will be considered
- 6. Approximately 50 to 100 minutes (min) later, a CT (transmission scan) will be obtained from vertex to midthighs for anatomical reference and attenuation correction purposes. This will be followed by a static PET emission scan over the same area, starting from mid thighs Refer to imaging charter and/or site imaging manual for details

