8.3.2 Histopathology assessments

In the cases where pathology will be available (from prospective biopsy or salvage surgery performed within 8 weeks after the completion of [18F]CTT1057 PET/CT scan and after the completion of [68Ga]Ga-PSMA-11 PET/CT scan), assessments by the local pathologists will be performed as per SoC, and results are to be provided within 2 weeks of the biopsy. Pathologists will be blinded to any PSMA-PET data (i.e. both PET/CT scans), but not to other patient data.

Pathology data to be documented in eCRF will include among others the procedure/methodology used, the outcome of the assessment, i.e. if negative or positive for adenocarcinoma, if other tumor histological types are present or not and their nature, number, location as well as size of the tumor and/or metastatic lesions within the tissue specimens.

8.3.3 **PSA level assessments**

For CTS Level 3, increases and decreases of PSA levels will be tracked to assess PSA responses before and after RT (third component of the CTS) as per PCWG3 for participants where pathology or radiological assessments are not available or conclusive.

RT should commence within approximately 8 weeks of completing the study treatment (i.e. both PET/CT scans) and PSA should be assessed prior to starting the RT and then at approximately 90 days from last day of radiation.

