#### **Additional Follow-up**

Additional follow up period will be applicable where additional diagnostic procedures are to be performed. These may include SoC pathology, imaging or other modality disease assessments (CTS Levels 1 or 2) up to 8 weeks after [18F]CTT1057 PET scan or three-month follow-up imaging (from baseline) where it is clinically required for the diagnosis of particular lesion(s).

In addition, in cases where the CTS Level 2 is not feasible/appropriate, the CTS Level 3 will apply and will include the assessment of PSA levels prior to starting radiotherapy (which should commence within 8 weeks of completing [F]CTT1057 PET scan) and at approximately 90 days from last day of radiation.

PSA response per PCWG3 is defined as a 50% or greater decline in PSA on the post-RT timepoint compared to PSA prior to RT. If a participant has PSA response, in the absence of concomitant androgen deprivation therapy administration, then the irradiated lesion (recorded in the concomitant antineoplastic – radiotherapy CRF page) will be considered as a confirmed prostate cancer lesion.

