#### 2.5.5 Sensitivity analyses

For participants where CTS Level 1 or 2 is used as the truth standard for the primary analysis, the next lower level of CTS will be used to verify positivity or negativity for the sensitivity analysis, if available. For instance, if pathology (CTS Level 1) is used for a lesion as the truth standard for the primary estimand, the imaging component of CTS (Level 2) will be used as truth standard for sensitivity analysis for the primary estimand. Similarly, results of CTS Level 2 will be replaced by CTS Level 3 if applicable. However, for those using changes in PSA level (CTS Level 3) as the truth standard for primary estimand, their positivity status cannot be replaced by another component of CTS for sensitivity analysis.

Region-level CLR along with its 95% CI will also be computed based on the weighted estimator approach (Lee and Dubin 1994) for each central reader as following:

$$\hat{p}_w \pm 1.96 \hat{\sigma}/\sqrt{n}$$
.

 $\hat{p}_w$  is the point estimator with  $\hat{p}_w = \sum_{i=1}^n \hat{p}_i / n$  and  $\hat{p}_i = y_i / n_i$ , where  $y_i$  and  $n_i$  are the same as defined in Section 2.5.2 above and n represents the number of participants with at least one PET-positive finding by central assessments.  $\hat{\sigma}$  is the estimated standard deviation of  $\hat{p}_i$ .

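### The protocol and SAP do not keep histopathology from the Level 2 truth readers, so agreement in the Level 1-to-Level 2 sensitivity analysis may be partly built in

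*Protocol*

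**What the plan says.** Three protocol sections set the rule for the central Level 2 readers.

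- Section 6.4: "blinded to [18F]CTT1057 PET/CT images, but not to other patient data collected in clinical database".
- Section 4.1: "blinded to [18F]CTT1057 PET/CT scan results, but not to other patient data".
- Section 8.3.1: "blinded to [18F]CTT1057 PET/CT scan results, but not to other patient data collected in" the clinical database.

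None of them lists the forms a reader may or may not see, or fixes when the read takes place relative to data entry. Section 8.3.1 defers the rest: "Further details will be provided in the Imaging Charter". SAP 1.1 refers back to the protocol for reading and blinding and adds no restriction.

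On what is collected, protocol 8.3.2 states: "Pathology data to be documented in eCRF will include among others the procedure/methodology used, the outcome of the assessment", together with the number, location and size of lesions. SAP 1.1 (Additional Follow-up) says that after a PSA response "the irradiated lesion (recorded in the concomitant antineoplastic – radiotherapy CRF page) will be considered as a confirmed prostate cancer lesion", so a CRF page identifies the irradiated lesion.

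Level 2 is the truth standard where pathology is missing, inconclusive or a negative biopsy. It also serves as a check on Level 1. Under SAP 2.5.5, "if pathology (CTS Level 1) is used for a lesion as the truth standard for the primary estimand, the imaging component of CTS" takes its place in the sensitivity analysis.

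**The concern.** Changing the truth standard is informative only if the two standards were reached separately. A Level 2 reader who already knows the tissue result for a lesion is not giving a second opinion on it. Agreement between the primary and the sensitivity result would then say less than it appears to about whether CLR and PPV depend on the choice of standard.

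The protocol guards against this elsewhere. The [18F]CTT1057 readers are blinded to patient data, including histopathology, and the pathologists are blinded to both PET scans. Only the Level 2 readers, who decide truth for most lesions, have an open-ended set of data.

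A second and smaller worry is that information prompted by the [18F]CTT1057 scan could reach the truth read indirectly, through where a patient was later treated.

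**Working it through.** The plan gives no figure on this point, so the check sets the sections side by side and sizes the group affected.

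**1. What a Level 2 reader may see**

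| Item | In the clinical database? | Identifies a site? | Masked from Level 2 readers? |
|---|---|---|---|
| Histopathology | Yes, explicit (protocol 8.3.2) | Yes | No |
| Irradiated lesion | Yes, explicit (SAP 1.1) | Yes | No |
| Local [18F]CTT1057 read | Protocol 8.3.1 puts PET/CT outcome and lesion location in the eCRF and does not exempt it | Yes | Yes under 4.1 and 8.3.1, which refer to scan results; not clearly under 6.4, which refers to images |
| Questionnaire 2 | Inferred: SAP 2.1 analyses data from the database and SAP 2.6.1 tabulates the questionnaires; the row in protocol Table 8-1 carries timing text, not the database code | No; the options are treatment categories, and only the free-text option could name a site | No |

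**2. Which lesions the swap touches.** A negative biopsy passes to Level 2 in the primary analysis. Level 1 therefore stands as primary truth for positive biopsies and for conclusive surgical specimens. These are the lesions whose pathology SAP 2.5.5 replaces, and on these the written rule lets the reader see the result being replaced.

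**3. How many patients.** Protocol 4.1 expects pathology in about 35-40% of patients, and in only some of their lesions. Assuming that share holds in the 152 evaluable patients:

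- 0.35 × 152 = 53.2
- 0.40 × 152 = 60.8

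That gives about 53 to 61 patients. The number touched by the swap is lower to the extent that their only pathology is a negative or inconclusive biopsy.

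**4. Timing.** Biopsy or surgery follows both PET scans and falls within 8 weeks of the [18F]CTT1057 scan, with results due 2 weeks later: 8 + 2 = 10 weeks. Level 2 may include three-month follow-up images. Pathology can therefore be on file before the Level 2 read is complete, and nothing fixes the order.

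**5. Direction.** A visible positive specimen or irradiated site would pull a doubtful call towards cancer. A visible negative biopsy would pull the other way, and for those lesions Level 2 is the primary truth. The documents give no means of netting these effects.

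**The case against.** The strongest reply has four parts.

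- **The charter may settle it.** The protocol defers reading details to the imaging charter, which may define a restricted reader package. The protocol permits access; it does not show that readers were given every form. This stands, and it is why the point is that independence is not secured, rather than that it was lost.
- **Context is legitimate.** Readers of a composite standard need clinical information, and three-month images may be uninterpretable without knowing that treatment intervened. This stands, and it rules out withholding all treatment data.
- **Two of three readers must agree.** This helps little, because all three work under the same access rule.
- **The swap concerns a minority of lesions.** True. It limits the reach of the problem but does not remove it.

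A reader might infer something stronger: that the reference standard follows the index test and inflates both co-primary endpoints. The documents do not support that. Sections 4.1 and 8.3.1 mask the [18F]CTT1057 results. Questionnaire 2 has no site field, and its place in the database is inferred. Only a radiotherapy page is shown to identify a treated lesion; no surgery page is. Protocol section 3 says a change of management should not rest on [18F]CTT1057 alone, and treated sites also reflect the [68Ga]Ga-PSMA-11 scan, which Level 2 readers see anyway. What remains is site information for lesions positive on [18F]CTT1057 only.

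A figure can be attached to the stronger reading, but only by assumption. Take a true PPV at the 0.20 threshold, 152 × 0.80 = about 122 PET-positive patients, and success at 34 or more true positives. If 5% of false positives were relabelled, the observed PPV would be 0.20 + 0.80 × 0.05 = 0.24, and one reader's chance of passing on PPV would rise from 2.3% to 18.4%. Neither the 5% nor the one-way direction comes from the documents, so this is not an estimate of bias in this trial.

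**Conclusion.** The point holds as a weakness in the written blinding rule. As the protocol and SAP stand, the Level 2 read is not protected from the pathology it is meant to replace, and agreement in the SAP 2.5.5 analysis may be partly built in. The analysis would still tell something: a Level 2 call that contradicted known pathology would be informative. It is agreement that loses weight.

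The indirect route from [18F]CTT1057 to the Level 2 read is a lesser risk, confined to lesions positive on that tracer alone. The net effect on PPV and CLR has no established direction, and no magnitude can be taken from the documents. The conclusion assumes that the charter does not already restrict the reader package; if it does, the remaining task is to bring the protocol and SAP into line with it.

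**What to change.** In protocol 4.1, 6.4 and 8.3.1 and in the imaging charter, state that the Level 2 read is made and locked without:

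- histopathology;
- any [18F]CTT1057 result, local or central, with the reference to images in 6.4 aligned to the reference to scan results in 4.1 and 8.3.1;
- questionnaire 2;
- the target site of any post-scan treatment.

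Baseline history, prior therapy and PSA stay available. For follow-up images, the type and dates of intervening treatment may be given without the target site.

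In SAP 2.5.5, state that the Level 2 result used is this locked read. The SAP amendment of 20-Dec-2023 was written shortly before database lock, so reads may already have been made. If they were made with open data, record what the readers saw and qualify the sensitivity analysis accordingly.

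The cost is wording in the protocol, charter and SAP. No reader, procedure or patient is added, and the sample size, thresholds and significance level are unchanged. The downside is that truth readers lose some clinical context for doubtful lesions.
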